	
 Planned medical or surgical intervention Treatment with anti-angiogenetic drugs within 3 months prior randomization for study eye and 1 month for fellow eye Intravitreal steroids in phakic eye or without sufficient time since last treatment (at least 3 months, for dexamethasone implant 6 months or 3 years for fluocinolone implant 
Systemic conditions or treatments
 
 History of stroke within 4 months prior to enrollment. Untreated diabetes mellitus. Blood pressure systolic > 160 mmHg or diastolic > 100 mmHg Pregnant and nursing women and women physiologically capable of becoming pregnant, unless they are using effective methods of contraception
Investigational and reference therapy	The investigational treatment in this study is 0.5 mg ranibizumab 10 mg/ml solution for injection, supplied in prefilled syringes (PFS). If PFS are not available vials will be used.
Efficacy assessments	
 Best Corrected Visual Acuity (ETDRS) Spectral Domain Optical Coherence Tomography Color Fundus Photography
Safety assessments	
 Adverse events Vital signs Standard ophthalmic examinations (including ophthalmoscopy, slit lamp, intraocular pressure, gonioscopy)
Key other assessments	
 [REDACTED] [REDACTED] [REDACTED]
Data analysis	
The primary objective of this trial is to demonstrate, that the ranibizumab treatment at the discretion of the investigator (DI) is non-inferior to ranibizumab PRN treatment with respect to the mean average BCVA change from baseline to month 12.
 
However as the assumed patient number for primary outcome will not be reached the data analysis will be purely exploratory.
 
The following hypothesis will be tested at a one-sided 0.025 level.
 
Non-inferiority with respect to BCVA:
 
$H_0: \mu_{DI} - \mu_{PRN} \leq -\Delta$ versus $H_A: \mu_{DI} - \mu_{PRN} > -\Delta$
 
where μ_{DI} and μ_{PRN} are the unknown mean average changes from baseline in BCVA to month 12 in the DI regimen and the PRN regimen, respectively. Δ is the non-inferiority margin and is pre-

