9.7 Sample size calculation

A sample size of 133 patients per treatment arm will have 90% power to establish non-inferiority at a margin of 4 letters for the 0.5 mg ranibizumab “at investigators discretion” dosing regimens in comparison to 0.5 mg ranibizumab PRN in the mean average change in BCVA based on a one-sided 0.025 significance level, assuming a treatment difference of 0 letters, a standard deviation of 10 letters and an underlying normal distribution for an unstratified t-Test (nQuery Advisor 7.0).

The Phase III study (RESTORE) results in the FAS suggest a mean average change in BCVA of 6 letters with a standard deviation of about 7-8 letters for ranibizumab. To account for some more variability related to the retreatment concepts and subgroup treated with additional PRP laser in this study as compared to RESTORE, a standard deviation of 10 letters is assumed. To account for some drop outs 150 patients will be randomized per treatment arm.

Due to reasons mentioned in section “Summary of protocol amendments” recruitment will be terminated, resulting in a reduced sample size present for analysis.

As a consequence results are to be interpreted in a purely descriptive manner. With an estimate of about 120-150 patients to be enrolled by end of recruitment the expected power would be about 55-60% and will be evaluated accordingly.

10 Ethical considerations**10.1 Regulatory and ethical compliance**

This clinical study was designed and shall be implemented and reported in accordance with the ICH Harmonized Tripartite Guidelines for Good Clinical Practice, with applicable local regulations (including European Directive 2001/20/EC, US Code of Federal Regulations Title 21, and Japanese Ministry of Health, Labor, and Welfare), and with the ethical principles laid down in the Declaration of Helsinki.

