## 2.6.2 Statistical hypothesis, model, and method of analysis

As a consequence of the early recruitment termination, all analyses will be interpreted in a purely descriptive manner. Nevertheless, the planned non-inferiority hypothesis testing of the ranibizumab injections at the discretion of the investigator (DI) and ranibizumab injections of current standard care (PRN) for patients with DME will still be performed.

The following hypotheses related to non-inferiority at a one-sided 0.025 significance level will be performed:

Null hypothesis:  $H_0: \mu_{DI} - \mu_{PRN} \leq -\Delta$

Alternative hypothesis:  $H_A: \mu_{DI} - \mu_{PRN} > -\Delta$

where  $\mu_{DI}$  and  $\mu_{PRN}$  are the unknown mean visit-averaged change from baseline in BCVA from month 1 to EoT, in the DI regimen and the PRN regimen, respectively.  $\Delta$  is the non-inferiority margin and is predefined to be 4 letters. The hypothesis testing with respect to non-inferiority of BCVA will be carried out using an analysis of covariance (ANCOVA) model including study treatment (DI, PRN) and center as factors and baseline BCVA as continuous covariate.

The Least Square (LS) (“adjusted”) means for each treatment arm and estimates of the difference (DI - PRN) will be given along with the respective two-sided, 95% CI and the p-value for the (unshifted) null hypothesis ( $\mu_{DI} - \mu_{PRN} = 0$ ).

The one-sided non-inferiority p-value for the shifted hypothesis ( $\mu_{DI} - \mu_{PRN} \leq -\Delta$ ) will be calculated. Non-inferiority will be claimed, if the lower limit of the two-sided 95% CI (equivalent to the one-sided 97.5% CI) does not exceed  $-\Delta$  (i.e. -4 letters).

There are no multiplicity issues as there is only one primary comparison.

The key assumptions that underlie the use of ANCOVA model for the primary analysis will be checked. The normality assumption of the error term will be performed and in case of clear deviations, a non-parametric comparison – Wilcoxon Rank Sum Test – will be performed instead of ANCOVA for the primary analyses. Homogeneity of variance between/ among treatment arms will be evaluated visually.

At each visit, descriptive statistics will be provided for the following values of the primary efficacy variable BCVA by visits and treatment arms:

- Baseline
- Absolute and change from baseline
- Visit-averaged change from baseline in BCVA from month 1 to EoT

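### The primary decision sentence still says non-inferiority will be claimed although the plan calls the analysis purely descriptive, and its wording of the criterion is the reverse of the alternative hypothesis

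*SAP*

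**What the plan says.** **Status.** SAP 2.6.2 opens: "As a consequence of the early recruitment termination, all analyses will be interpreted in a purely descriptive manner". SAP 1.1, 2.1 and 3 repeat the exploratory or descriptive status. In the protocol, the data analysis part of the synopsis says "the data analysis will be purely exploratory", and section 9.7 says "results are to be interpreted in a purely descriptive manner".

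**Test.** The next sentence of SAP 2.6.2 keeps the test: "Nevertheless, the planned non-inferiority hypothesis testing of the ranibizumab injections" will still be carried out. SAP 2.1 likewise says that testing goes ahead.

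**Decision rule.** Further down in SAP 2.6.2: "Non-inferiority will be claimed, if the lower limit of the two-sided 95% CI" ("equivalent to the one-sided 97.5% CI) does not exceed" minus delta, spelled out as -4 letters). On delta, the section says it "is the non-inferiority margin and is predefined to be 4 letters". The protocol synopsis and protocol 9.4.2 contain the same rule. In the synopsis it follows the exploratory statement directly. In 9.4.2 it stands without any caveat, and the descriptive statement appears only in 9.7.

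**Hypotheses.** In all three places the null is a DI minus PRN difference at or below -4 letters, and the alternative is a difference above -4.

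**The concern.** There are two faults in one sentence.

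First, computing an interval and a shifted p-value fits a descriptive report; announcing that non-inferiority is claimed does not. The words that keep the analysis alive concern testing. They do not mention claims. A report writer could cite the decision rule to present a favourable interval as established non-inferiority, or cite the descriptive statement to set aside an unfavourable one, and the plan would not rule out either choice.

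The room for choice is wider than one interval. SAP 2.6.4 gives the shifted p-value for every supportive and sensitivity analysis that reports p-values, and treats the per-protocol result as almost as important as the full-analysis-set result. Several results will therefore be set against -4 letters with no stated status. SAP 4 records no change from the protocol, so it does not help.

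Second, the direction is wrong as written. A lower limit that does not exceed -4 leaves the margin inside or above the interval, which is the case where non-inferiority has not been shown.

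**Working it through.** **1. Inputs.** SAP 3 and protocol 9.7: margin 4 letters, SD 10, true difference 0, one-sided 0.025, 133 per arm for 90% power, 150 per arm randomized to allow for dropout. SAP 1.1 and 3: 135 patients, 1:1. The originally planned total was 300, so 135/300 = 45%.

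**2. The plan's own figure.** The normal approximation gives n per arm = 2 x (1.960 + 1.282)^2 x 10^2 / 4^2 = 131.4, rounded up to 132. The noncentral t-test gives power 0.899 at 132 and 0.901 at 133. The stated 133 per arm is reproduced.

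**3. Precision at 135 patients** (even split, no dropout):

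- Standard error = 10 x sqrt(4/135) = 1.721
- Half-width = t(0.975; 133 df) x SE = 1.978 x 1.721 = 3.40 letters
- For a lower limit above -4, the estimate must exceed -4 + 3.40 = -0.60 letters

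**4. How often the intended criterion is met if the true difference is 0.** Noncentrality = 4/1.721 = 2.324. The noncentral t with 133 df gives 63.6% (normal approximation 64.2%). Using the dropout allowance implied by the plan, (150 - 133)/150 = 11.3%, the figure is 58.3%. With no dropout, the plan's range of 120 to 150 patients gives 58.4% to 68.2%.

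These are power figures. They do not measure the defect. They show only that meeting and missing the criterion are both realistic, so the status of a met criterion is a practical question. If the true difference is -4, the intended criterion is met 2.5% of the time at any size, so the smaller sample does not change the error rate.

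**5. Direction of the rule.** Taking the half-width of 3.40:

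| Estimate (DI - PRN) | 95% CI | Alternative hypothesis (limit above -4) | Rule read literally (limit not above -4) |
|---|---|---|---|
| 0 | -3.4 to 3.4 | supported | no claim |
| -3 | -6.4 to 0.4 | not supported | claim |

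If the true difference were -4, the literal rule would be met 97.5% of the time instead of 2.5%.

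**6. Status, place by place.**

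| Place | Status declared | Claim rule kept | Status of a met criterion |
|---|---|---|---|
| SAP 2.6.2 | descriptive | yes | not stated |
| Protocol synopsis | exploratory | yes | not stated |
| Protocol 9.4.2 | none there; descriptive in 9.7 | yes | not stated |

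**The case against.** The best reply is that the status is already fixed. SAP 2.6.2 applies the descriptive reading to all analyses before it introduces the test, and SAP 2.1 and 2.8.2 use the same order: limited interpretation, test still run. On that reading the rule is a leftover from the full-size design and the test is kept only as a calculation. This is probably what was meant, and the pairing of test and descriptive status is open and deliberate. What it leaves unanswered is the verb. Keeping a test is not the same as keeping a claim, and no section says that the claim lapses.

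A reader might infer that the plan allows two opposite conclusions from one result. The conflict over status does not support that. A descriptive reading limits the weight of the result; it does not conclude inferiority or failure.

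A reader might also infer that the sponsor would really claim non-inferiority on a poor interval because of the reversed wording. The documents do not support that either. The stated hypotheses, the shifted p-value and the code note in SAP 5.2.1 (subtract 4 letters from control, upper-tailed comparison) all point in the intended direction. The reversal is a drafting error, but it sits in the sentence that decides the primary result.

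It is also fair to say that the low power is disclosed (about 55-60% in SAP 3 and protocol 9.7) and that rewording alters no estimate, interval or p-value.

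**Conclusion.** The point holds as a matter of status and wording. The primary decision sentence conflicts with the declared status of the analysis, no section resolves this, and its literal direction contradicts the alternative hypothesis. The plan leaves open whether a met criterion supports a claim, and that could be decided once the result is known. The documents do not support an inference of an inflated error rate: the test in its intended direction stays at 0.025 one-sided.

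The context figures (half-width about 3.4 letters, criterion met about 64% of the time) assume 135 patients evenly split, SD 10, no true difference, no dropout and a plain t-test. The planned ANCOVA also fits centre and baseline BCVA. The number of centres contributing patients is not stated, so no figure is offered for that model. The conclusion does not depend on these numbers.

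**What to change.** In SAP 2.6.2, and in the protocol synopsis and section 9.4.2 if the protocol is amended, replace the decision sentence with:

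> The estimate and two-sided 95% CI will be reported against the -4 letter margin. A lower limit above -4 will be described as excluding a deficit of 4 letters or more; otherwise the margin is not excluded. The one-sided p-value is descriptive and no confirmatory non-inferiority claim will be made, whichever way the result falls.

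This settles the status and corrects the direction together. It should be in place before the analysis team is unmasked at database lock. Calling a favourable limit merely compatible with non-inferiority would be too weak, because an interval that crosses -4 is compatible with it too.

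The cost is a short text change; every planned estimate, interval and p-value stays. The sponsor gives up a formal claim that its own text already treats as descriptive only. If it does want that claim, it should say so in advance, qualify the descriptive statements, and still correct the direction.

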9.4.4 Supportive analyses

The primary analysis will be repeated for the PPS using the same model as the one used for the primary analysis.

The change from baseline in BCVA will be compared between the two treatments based on the assumption of a “Missing at Random (MAR)” process, i.e. assuming that the statistical behavior of a patient who drops out post-withdrawal is the same as that for a patient remaining in the study and sharing the same covariates and the same measurement history.

Gender subgroup analysis will be done for primary objective and key secondary objectives.

[REDACTED]
[REDACTED]
[REDACTED] and [REDACTED]

[REDACTED]

[REDACTED]

In case of significant outliers or deviations from normality assumptions, a nonparametric comparison (Wilcoxon Test) may be performed additionally to the primary analyses.

Further details about the models and analyses will be given in the statistical analysis plan. Any major discrepancies in the results across analyses will be investigated as needed.

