## 3 Sample size calculation

A sample size of 133 patients per treatment arm will have 90% power to establish non-inferiority at a margin of 4 letters for the 0.5 mg ranibizumab “at investigators discretion” dosing regimens in comparison to 0.5 mg ranibizumab PRN in the mean average change in BCVA based on a one-sided 0.025 significance level, assuming a treatment difference of 0 letters, a SD of 10 letters and an underlying normal distribution for an unstratified t-Test (nQuery Advisor 7.0).

The Phase III study (RESTORE) results in the FAS suggest a mean average change in BCVA of 6 letters with a SD of about 7-8 letters for ranibizumab. To account for some more variability related to the re-treatment concepts and subgroup treated with additional PRP laser in this study as compared to RESTORE, a SD of 10 letters is assumed. To account for some drop outs 150 patients will be randomized per treatment arm.

As outlined in the study protocol, section “Summary of protocol amendments” (study protocol version no.1 including Amendment 1); further recruitment of patients into this study was revised and reduced. New and relevant scientific evidence regarding treatment patterns with ranibizumab was published which did not justify continuing the trial with newly included

patients. Therefore recruitment was terminated at the time when 135 patients were enrolled into the study, resulting in a reduced sample size present for analysis.

As a consequence results are to be interpreted in a purely descriptive manner. With an estimate of about 120-150 patients to be enrolled by end of recruitment the expected power would be about 55-60% and will be evaluated accordingly.

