#### SAS code for ANCOVA analysis

ANCOVA model will contain ‘treatment’ and ‘center’ as categorical variables, and ‘baseline BCVA’ as continuous. For secondary analysis additional linear covariates might be included, such as ‘HbA1c’, ‘Blood pressure (systolic, diastolic)’, or ‘Lipid levels (cholesterol, HDL-cholesterol, LDL-cholesterol, triglycerides)’.

For the appropriate treatment difference, the treatment arms should be sorted or coded appropriately before using this model.

The ANCOVA analysis will be performed using SAS procedure PROC MIXED as below. Note that for this illustrative example:

- the data are stored in the file data\_set
- treatmentvar = treatment variable

- responsevar = dependent variable
- stratavar = stratification variable
- bsl = baseline value of the responsevar
- alpha = significance level (i.e. 0.05 produces two-sided 95% CI)
- control = control arm (Ranibizumab 0.5 mg in PRN treatment regime)

```
PROC MIXED DATA = <data_set>;
CLASS <stratavar> <treatmentvar>;
MODEL <responsevar> = <stratavar> <treatmentvar> <bsl>;
LSMEANS <treatmentvar> / PDIFF = all CL alpha = <alpha> OM;
RUN;
```

To get the one-sided p-value for the non-inferiority test (margin = 4): add -4 letters to control group and re-run the above code with alpha=0.025 and PDIFF=controlu('<control>').

To get the one-sided p-value for the superiority test (if applicable): re-run the above code with alpha=0.025 and PDIFF=controlu('<control>').

---

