### SAS code for Wilcoxon rank sum test

Wilcoxon Rank Sum Test will be presented as a nonparametric comparison additionally to the primary analyses.

For the appropriate treatment difference, the treatment arms should be sorted or coded appropriately before using this model.

Wilcoxon Rank Sum Test will be presented as a non-parametric comparison additionally to the primary analyses.

- the data are stored in the file data\_set
- treatmentvar = treatment variable
- responsevar = dependent variable
- alpha = significance level

```
PROC NPAR1WAY DATA = <data_set> HL alpha = <alpha>;
CLASS <treatmentvar>;
VAR <responsevar>;
RUN;
```

=====

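### The Wilcoxon fallback for the primary analysis is coded without the 4-letter shift, nothing ties its Hodges-Lehmann limit to -4, and the documents disagree on whether it replaces ANCOVA

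*SAP*

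**What the plan says.** SAP 2.6.2 sets the null as a mean DI minus PRN difference of -4 letters or lower, tested at one-sided 0.025. It bases the claim on the lower limit of the two-sided 95% interval from ANCOVA. It adds that, on clear departures from normality, the Wilcoxon rank sum test "will be performed instead of ANCOVA for the primary analyses".

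SAP 5.2.1 supplies the code. The ANCOVA section ends with this step: "To get the one-sided p-value for the non-inferiority test (margin = 4): add -4 letters to control group and re-run the above code". The MMRM section has the same step. The Wilcoxon section has none. Its procedure line is "PROC NPAR1WAY DATA = <data_set> HL alpha = <alpha>", followed by the treatment class and the response variable, and it describes alpha only as a significance level.

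On the status of the test, Protocol 9.4.4 says that "a nonparametric comparison (Wilcoxon Test) may be performed additionally to the primary analyses". The Wilcoxon code section of the SAP also states, twice, that the test is presented in addition to the primary analyses. SAP section 4 reports no change from the protocol-specified analysis.

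**The concern.** Once Wilcoxon stands in for ANCOVA, its output is the primary result. Run as coded, the procedure prints a p-value for equality of the two arms. A small p-value with DI worse points towards inferiority. A large one says nothing about the margin. Neither tests the stated null.

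The same output contains a usable quantity, the Hodges-Lehmann shift with its interval, but the SAP never says that this interval decides. Its level is also open. The ANCOVA, MMRM and backward-regression sections explain that alpha = 0.05 gives a two-sided 95% interval; the Wilcoxon section does not. Entering the stated test level of 0.025 would give a 97.5% interval.

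The unclear status matters because SAP 2.6.4 promises a shifted p-value for supportive and sensitivity analyses. That promise covers Wilcoxon if it is additional, but not if it is the primary analysis.

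**Working it through.** **Inputs.** From SAP section 3: the design is "based on a one-sided 0.025 significance level, assuming a treatment difference of 0 letters, a SD of 10 letters"; "A sample size of 133 patients per treatment arm will have 90% power to establish non-inferiority at a margin of 4 letters"; and "recruitment was terminated at the time when 135 patients were enrolled into the study". Allocation is 1:1 (SAP 1.1), taken here as 67 DI and 68 PRN. The distribution shapes are assumptions: normal, t with 4 df, and left-skewed gamma with shape 2, each scaled to SD 10. Variances are equal and there is no dropout.

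**Plan's own figure.** n per arm = 2 × (10/4)² × (1.960 + 1.282)² = 12.5 × 10.51 = 131.4, so 132 by the normal approximation. The noncentral t calculation gives 133 (power 90.1%; 132 gives 89.9%). The stated 133 is reproduced.

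**What each Wilcoxon run tests.** Let x be D0 in DI and y be D0 in PRN.
- As coded: x against y. Null: shift = 0.
- With the ANCOVA step: x against y - 4, DI greater. Null: shift ≤ -4.
- Hodges-Lehmann: the interval is the rank sum test inverted, so a 95% lower limit above -4 should give the same decision as the shifted one-sided test at 0.025.

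**Closed-form check, normal data.** Noncentrality = 4 / (10 × √(1/67 + 1/68)) = 2.324. Multiply by √(3/π) = 0.977 for the Wilcoxon efficiency: 2.271. Power of the shifted test at true difference 0 = Φ(2.271 - 1.960) = Φ(0.311) = 62%. The unshifted two-sided test at true difference -4 is the mirror image, so it is non-significant in about 100 - 62 = 38% of trials.

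**Simulation, 60,000 trials per case.**

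| Shape | Unshifted, one-sided 0.025, rejects at 0 | Shifted rejects at 0 | Shifted rejects at -4 | Unshifted, two-sided 0.05, non-significant at -4 |
|---|---|---|---|---|
| Normal | 2.6% | 61.6% | 2.5% | 38.6% |
| t, 4 df | 2.5% | 77.0% | 2.5% | 22.6% |
| Skewed | 2.4% | 78.7% | 2.4% | 21.0% |

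Smaller runs of 10,000 trials agree within about 2 percentage points. For the last column they give 38% to 40% under normality and 21% to 23% otherwise, which is the source of the 21% to 40% range.

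**Agreement of the two correct routes.** In 10,000 trials per case (normal and t4; true differences 0, -2 and -4), the 95% Hodges-Lehmann lower limit and the shifted test gave the same decision every time.

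**Effect of alpha.** With alpha = 0.025 in the Hodges-Lehmann request, the chance of clearing -4 at true difference 0 falls from about 62% to about 50% (normal data).

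**Status of the test, side by side.**

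| Place | Wilcoxon is |
|---|---|
| SAP 2.6.2 | a replacement for ANCOVA |
| SAP 5.2.1, Wilcoxon section | additional |
| Protocol 9.4.4 | optional and additional |
| SAP section 4 | no change from protocol |

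The first row cannot stand together with the other three.

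**The case against.** The best defence is that the SAP decides from an interval, and the coded procedure produces one. SAP 2.6.2 fixes 95% two-sided for the decision, the other code sections tie alpha = 0.05 to that level, and the Wilcoxon section says the arms must be coded for the right difference. The hypotheses are stated before the fallback and are not withdrawn. The code is a template with placeholders. If Wilcoxon is additional, SAP 2.6.4 already requires a shifted p-value. SAP 2.6.2 gives no route to a non-inferiority claim from a non-significant difference test.

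Much of this stands. A reader might infer that the fallback cannot answer the primary question at all. The documents do not support that, because the Hodges-Lehmann interval is requested and its 95% lower limit reproduces the shifted test. A reader might also contrast 2% to 3% rejection for the unshifted test with 62% to 79% for the shifted one and call it lost power. It is not: the two tests address different nulls, and an unshifted test at no difference rejects at its own level by construction.

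What remains is that the interval rule in SAP 2.6.2 is written for the ANCOVA contrast and is nowhere extended to Hodges-Lehmann. The intention to shift is not carried into the Wilcoxon code, even if SAP 2.6.4 applies. And whether SAP 2.6.4 applies depends on a status that the documents state both ways.

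**Conclusion.** The point holds as a mismatch between hypothesis and code, together with a contradiction over the role of the test. The coded Wilcoxon p-value tests equality. At a true 4-letter deficit it is non-significant in roughly 21% to 40% of trials, so it cannot serve as the non-inferiority test. Either correct route keeps the error at the margin near 2.5% and succeeds in about 62% to 79% of trials when the regimens are equal.

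These figures rest on SD 10, 135 evaluable patients, equal variances and the assumed shapes. The normal case is only a reference, since the fallback is meant for non-normal data; the two non-normal shapes give 21% to 23%. That the HL option yields the Hodges-Lehmann shift and interval is standard SAS behaviour, not explained in the SAP. The Wilcoxon comparison also drops center and baseline BCVA and estimates a location shift, not a difference in means.

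The impact is limited. The fallback applies only if normality clearly fails, and SAP 2.6.2 declares all analyses purely descriptive. It also keeps the hypothesis test and the claim rule, so the fallback should still test what is stated.

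**What to change.** 1. Reconcile SAP 2.6.2 with the Wilcoxon section of SAP 5.2.1 and with Protocol 9.4.4. If Wilcoxon does replace ANCOVA, list this in SAP section 4 as a change from the protocol.
2. In the Wilcoxon section of SAP 5.2.1, add -4 letters to D0 in the PRN arm, re-run the procedure, and report the one-sided p-value (DI greater) at 0.025 as the non-inferiority p-value. Keep the unshifted p-value only as the counterpart of the unshifted ANCOVA p-value.
3. State that the Hodges-Lehmann interval is for DI minus PRN, uses alpha = 0.05 (two-sided 95%), and supports non-inferiority only if its lower limit lies above -4.

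The cost is a few sentences and one extra run of the same procedure. No new data are needed. The only downside is one more p-value in the table.
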